
 Evaluate the safety of CIS-telehealth relative to inpatient and OCIC-in-person among children with similar CHRT scores. 	
 Time to first recurrence of a suicidal event Number of suicidal events Severity of suicidal ideation
Secondary	

 Examine the effectiveness of CIS-telehealth relative to inpatient and in-person OCIC among children with similar CHRT scores. 	
 Score from PROMIS Short Form v 1.0-General Life Satisfaction-Short Form 5a (to assess the parent's well-being) Score from PROMIS Parent-Proxy Life Satisfaction-Short Form 8a Score from PROMIS Pediatric Life Satisfaction-Short Form 4a Score from CHRT-SR at baseline and follow-up visits

 Assess patient and parent treatment satisfaction with CIS-telehealth relative to inpatient and in-person OCIC among children with similar CHRT scores. 	
 Score from Client Satisfaction Questionnaire (CSQ-8)
Tertiary/Exploratory	

 Does Telehealth CIS lead to greater reduction of emotional arousal or perceived stress levels in response to COVID-19 the pandemic 	
 Scores from the COVID-19 survey

CONFIDENTIAL

Overall Design: Observational Design

Number of Participants: CCHMC- 61; other 3 sites- 61 each; total- 244 from all 4 sites

Treatment Groups: Inpatient Psychiatric Treatment vs. Outpatient Crisis Intervention Clinic (OCIC) vs. Telehealth Crisis Intervention Services (CIS)

Duration: 12 Months (1 Years)

2. Introduction

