Scores on the CHRT were also significantly reduced by discharge with propensity scores (26.01 ± 10.43 vs. 16.72 ± 10.03 ; $p < .0001$) as well as active suicidal ideation scores (4.85 ± 3.63 vs. 1.91 ± 2.40 ; $p < .0001$) showing a marked improvement compared to baseline. Preliminary clinical outcomes at discharge from [name]'s OCIC and at six month follow-up were positive. Patients were improved at the time of discharge on self-report of depressive symptoms

and suicidal ideation and behavior. 286 of the 364 adolescents (or 78.57%) responded to the 6 month follow up questions. In total, 8.7% and 27.3% of the 286 respondents reported a suicide attempt and event, respectively, within 6 months of discharge from OCIC. Reattempt rates at 6 months were at 8.7%, with almost half these occurring within one month after discharge. Suicidal events (includes attempts, emergency room visits or hospitalization) at 6 months were at 27.3%. It is possible that the suicidal events were higher than attempts because the adolescents were following their safety plan and reaching out for professional support when suicidal ideation increases. Patients who made an attempt within the 6 month follow up period had a history of more previous attempts, higher self-report of depressive symptoms at discharge, and higher levels of active suicidal ideation (CHRT) at entry and exit.

Those patients who had a suicide event at follow-up were more likely to be female, had more previous attempts, and had higher self-reported and parent reported depression at entry in the program. Those with a suicidal event also had higher self-reported active suicidal ideation at entry into the program.

Due to the fact that telehealth CIS is only currently being widely used for mental health services in this population group, CHRT-SR and other follow up data is not currently known. This research will seek to fill in this gap of knowledge.

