Breach of confidentiality: There is a potential risk of loss of confidentiality. Consistent with the Federal guidelines, all patients and guardians will be informed of the federally mandated reporting laws for child abuse and neglect, verbally and in the written consent form. Therefore, if abuse or neglect is suspected, per institutional and legal standards and requirements, the Department of Human Services may be called if appropriate and indicated. Risks associated with this reporting include embarrassment, legal consequences, and removal of the child from home.

3. Specific Aims and Hypothesis

Specific Aims	Hypothesis

SA1: Evaluate the safety of CIS-telehealth relative to inpatient and OCIC-in-person among children with similar CHRT-SR scores.
	
 Our working hypothesis is that CIS-telehealth is associated with a greater risk of suicidal event relative to inpatient and in-person OCIC. Response is defined by a delay in first recurrence of a suicidal event and a lower number of suicidal events over 90 days and 180 days. Clinical Features: 
 Severity of suicidal ideation at baseline and over 180 days number of suicidal events at baseline only Substance use at baseline and over 180 days. Sociodemographic features: Age, Gender, Gender Identity, Type of insurance (Public, Private or none), Ethnicity, Race, or living with one biological parent, two biological parents, a stepparent, a relative, or other.

SA2: Examine the effectiveness of CIS-telehealth relative to inpatient and in-person OCIC among children with similar CHRT scores.
	
 Our working hypothesis is that CIS-telehealth will be associated with poorer reduction in emotional arousal and perceived stress levels in response to COVID-19 the pandemic relative to CIS-inpatient and CIS-in-person.

SA3: Assess patient and parent treatment satisfaction with CIS-telehealth relative to inpatient and in-person OCIC among children with similar CHRT scores.
	
 Our working hypothesis is that CIS-telehealth is associated with less patient satisfaction than inpatient and in-person OCIC among children with similar CHRT scores.

Exploratory Aim
	

[figure not shown]
Specific Aims	Hypothesis

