
SA4: As an exploratory aim, assess the demographics and potential barriers to treatment for a third comparator of the “no show” group who were placed in Telehealth, OCIC or inpatient treatment but never showed up or left the inpatient unit against medical advice (AMA). Please see section 6.2 Treatment Compliance to view plan regarding follow up for this “no show” group.
 
SA5: As an exploratory aim, assess the impact of the COVID-19 pandemic on social and emotional functioning.
	
 • The no show group (the third comparator) who did not arrive for any OCIC appointments or left AMA from inpatient treatment will differ from the other comparators with respect to the following barriers to treatment: 1) Age 2) Gender ⁵³⁻⁵⁶ 3) Type of Insurance (public insurance/no insurance/private) ⁶¹⁻⁶³ 4) Ethnicity (Hispanic/Non) ⁶⁴; 5) Race (African-American (AA) versus non-African American) ⁶⁵⁻⁶⁷; 6) Living with one biological parent, two biological parents, a stepparent, a relative, or other ^{68, 69} • The no show group will have significantly shorter time to first recurrence of a suicidal event and a larger number of suicidal events over 90 days and 180 days in comparison to the other patients. • We hypothesize that the levels of perceived stress and depressed mood have been increased amidst the COVID-19 pandemic.

4. Study Design

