4.1. Overall Design

The study conceptual framework is illustrated in Figure 1. Briefly, we have proposed an observational design. Eligible individuals will be identified during a crisis assessment, either in the emergency department or during an emergency phone or telehealth assessment. Once the individual has been assessed and assigned to the clinician for treatment, study staff will assess if the patient is appropriate for the study using the study eligibility criteria. Individuals who receive treatment in one of the following treatment arms will be eligible for this observation study: inpatient, in-person OCIC or telehealth crisis intervention service. Eligible individuals will be contacted by study staff to introduce and offer the study. If patient and guardian agree, they will complete surveys at baseline and every 2 weeks for 6 months to evaluate outcomes.

Figure 1

Clinical features will be measured with the CHRT-SR, Suicidal Event Form for START, and our short START-Clinical Features (CF) form at baseline and every two weeks (see Schedule of Events) to evaluate HTE's. A one time survey will be completed at week 2 that collects information related to the impact of COVID-19 on the family. To decrease clinician, patient, and family burden, the scales are self-report short forms. All START follow up forms will be sent to participants and guardians every 2 weeks via email prompts in REDCap and data will be collected upon return from participants. Study CRCs will make best efforts to contact families for reminder to complete data within the study milestone window, however completion at each milestone marker is not ensured due to nature of population group. Data will be collected when available. The research coordinators, a research team member, or clinicians will ensure the

completion of the Suicidal Event Form for START and the brief START-CF form based on EHR review and/or other sources of information (family and patients) within 72 hours of admission (baseline) to inpatient, telehealth CIS, or OCIC and every two weeks. The research coordinators will search the EHR for all hospitals (with permission and consent) on weekly basis for suicidal events which may have ICD-10-CM code.¹⁰⁰ We developed this plan based on feedback from patients, families, and clinicians.

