5.7. Screen Failures

Screen failures are defined as participants who consent to participate in the clinical study but are not subsequently included in the study. A minimal set of screen failure information is required to ensure transparent reporting of screen failure participants to meet the Consolidated Standards of Reporting Trials (CONSORT) publishing requirements and to respond to queries from regulatory authorities. Minimal information includes demography, screen failure details, eligibility criteria, and any serious adverse events (SAE).

Individuals who do not meet the criteria for participation in this study (screen failure) may be rescreened. Rescreened participants will be assigned the same participant number as for the initial screening.

6. Treatments

Study treatment is defined as psychiatric treatment within either Outpatient Crisis Intervention Clinic (OCIC), on an Inpatient unit, or telehealth crisis intervention services. Participants will be placed in the treatment setting by the assessing clinician. These therapeutic interventions are available whether or not the subject agrees to participate in the study.

Telehealth crisis intervention services (telehealth CIS) is defined as psychiatric services provided via telehealth services that is expected to be scheduled within 7 business days of the crisis assessment. Interventions can be with a social worker, therapist or psychiatrist. Services are not in person and occur over a computer video/phone system.

Inpatient treatment includes supportive individual therapy, improving patient's coping skills, family meetings about safety planning, and medication management.^{6-9, 81}

OCIC services include crisis psychotherapy/intervention, evidence-based screening/risk assessments, coordination of care/referral to an ongoing provider, short-term therapy/crisis treatment, safety planning, and/or referral and linkage to follow-up care. Treatment in OCIC may include group therapy, individual therapy, and/or family therapy, depending on the site. Please

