Dallas	
A crisis intervention appointment will entail:
 
1.Identification of current crisis and precipitants
 
2.Exploration of feelings/emotions using components of CBT, DBT and other therapies
 
3.Identification and exploration of coping
	
1.Family support (on an individual level)
 
2.Safety assessment and planning
 
3. Multi-family group, which includes family wellness, communication, strength building
 
4. Referral and connection to outpatient provider for continued care.
	
Group (9 hrs/week, which includes two teen groups and one multi-family group), Once weekly individual therapy (60 minutes)
	
Treatment duration is 4-6 weeks, Follow-up assessment phone calls at 1 month and 6 months post-discharge
	
Licensed Clinical Social workers, Licensed Professional Counselors, and child and adolescent psychiatrists for medication management; All of the above include trainees performing treatments under the supervision of licensed providers
	
First preference is direct admission to Inpatient Unit (either at our site or in the community); if after hours, refer patient to ED

	
skills and resources
 
4. Safety planning and assessment
 
5. Psychiatric evaluation and medication management, as needed
 
*Note: #2 and #3 above are done in both individual and group format throughout the course of treatment
					
--	--	--	--	--	--	--

Treatment Components

Inpatient

	Medication evaluation and management	Safety planning	Individual and family therapy	Skills groups	DBT program with skills group	Length of stay
Dallas	X	X	X	X		7 days
New York	X	X	X		X	8 days
Nationwide Children's	X	X	X	X		8 days
Cincinnati	X	X	X	X		6 or 7 days

Outpatient (OCIC)

	Group therapy	Individual and family therapy	Referral to psychiatrist for med management	Crisis stabilization/safety reassessment	Safety Planning	Parents attend skills class	Length of treatment
Dallas	X	X	X	X	X	X	4-6 weeks
New York		X	X	X	X		3 visits
Nationwide Children's		X	X	X	X		1-6 weeks
Cincinnati		X	X	X	X		1-6 weeks

Telehealth Crisis Intervention Services CIS

	Individual and family therapy	Referral to psychiatrist for med management	Crisis stabilization/safety reassessment	Safety Planning	Length of treatment
Dallas	X	X	X	X	4-6 weeks
New York	X	X	X	X	1-3 visits
Nationwide Children's	X	X	X	X	1-6 weeks
Cincinnati	X	X	X	X	1-6 weeks

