The main objective of the analysis plan for the COVID-19 survey is to evaluate whether the changes of levels of emotional dysregulation, anxiety, depressed mood, perceived stress levels, and other indicators of well-being, during the pandemic, are associated with the treatment outcome. Furthermore, we will evaluate whether the changes of these indicators are associated with the perceived level of social support, disruptions in life events, and electronic media habits. First, the changes of levels of emotional dysregulation, anxiety, depressed mood, perceived stress levels, and other indicators of well-being, will be treated as covariates in the analysis under Aims 1-3 (comparative treatment effect analysis). Second, we will then use generalized linear model to evaluate the relationship between continuous outcomes and predictors and ordinal logistic regression model to evaluate the relationship between ordinal outcomes and predictors. The outcomes include the changes of levels of emotional dysregulation, anxiety, depressed mood, perceived stress levels, and other indicators of well-being, and the predictors include perceived levels of social support, disruptions in life events, and electronic media habits.

Interim analysis:

We propose to evaluate the progress of the project at the end of the 6th month. The goal of the interim analysis is to examine the following outcomes: 1) scores from PROMIS Short Form v 1.0-General Life Satisfaction-Short Form 5a (to assess the parent’s well-being), 2) scores from PROMIS Parent-Proxy Life Satisfaction-Short Form 8a, 3) Score from PROMIS Pediatric Life Satisfaction-Short Form 4a, 4) Score from CHRT-SR at baseline and follow-up visits.

Specifically, the change in CHRT-SR scores will be used to facilitate the decisions for revising the protocol. If any of the three treatment groups is found to have statistically significant lower

CONFIDENTIAL

levels of changes in CHRT-SR scores within the first six months with an effect size Cohen's $d > 1.2$ (which is considered as a "very large" effect size according to Sawiloski (2009)¹⁰⁹ in comparison with another treatment group, we will discuss the results with all steering committee members and the DSMB to decide whether we should recommend to psychiatry leadership that the treatment group with overtly inferior treatment outcomes should be discontinued at the four sites.

10. References

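### Section 9.2.3 adjusts the Aims 1-3 treatment comparisons for stress, mood and anxiety changes taken from a single week-2 survey, after treatment has normally begun, and does not say whether those adjusted models are the main ones

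*Combined protocol and SAP*

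**What the plan says.** The survey part of Section 9.2.3 (Other Analyses) concerns changes during the pandemic in emotional dysregulation, anxiety, mood, stress and similar measures. Its first analytic step reads: "and other indicators of well-being, will be treated as covariates in the analysis under Aims 1-3 (comparative treatment effect analysis"). This is worded as something that will be done, and it names the comparative models.

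Section 4.1 fixes when the survey is taken: "A one time survey will be completed at week 2 that collects information related to the impact of COVID-19 on the family". Section 8 and the Schedule of Events (Appendix 1) agree, with one administration at week 2 and none at baseline.

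Two places treat perceived stress as a possible result of treatment setting. The synopsis asks: "Does Telehealth CIS lead to greater reduction of emotional arousal or perceived stress levels in response to COVID-19 the pandemic". The SA2 hypothesis in Section 3 expects telehealth to show "poorer reduction in emotional arousal and perceived stress levels in response to COVID-19 the pandemic".

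The models also appear without the survey variables. Section 9.2.1 gives a Cox model with treatment option as the predictor. The Aims 1-3 paragraph of Section 9.2.3 repeats the Cox model for Aim 1 and gives age, gender and triage location as example covariates for the Aims 2 and 3 models.

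**The concern.** This is a non-randomised comparison, so the choice of covariates largely decides what the treatment contrast means. A covariate fixed before treatment can remove confounding. A covariate that treatment may already have changed can remove part of the effect under study, or bring in new bias if it shares unmeasured causes with the outcome.

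Aim 1 has a second problem. A Cox model with a fixed covariate assumes the value is known from time zero. With a week-2 value, a suicidal event on day 5 would be explained by a stress report made on day 14, and that report may itself reflect the event.

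Aim 1 is the safety comparison. Two analysts working from the same document could fit different models for it, and the models answer different questions if setting has moved stress or mood by week 2.

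**Working it through.** **Step 1. Has treatment started by week 2?**

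- Telehealth: the first contact is "expected to be scheduled within 7 business days of the crisis assessment" (Section 6). Counted from any day of the week and ignoring holidays, 7 business days is 9 to 11 calendar days.
- In-person OCIC: Section 6 gives the same 7-business-day expectation, counted from the ED visit. Section 2.2 says within three days of the crisis.
- Inpatient: the site table in Section 6 lists stays of 6 to 8 days.
- Baseline forms are completed within 72 hours of admission to the arm (Section 4.1).

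All of these precede day 14, so the survey normally follows the start of treatment in every arm. The stage of care differs. A typical inpatient stay is over, while for the Dallas OCIC "Treatment duration is 4-6 weeks", and Dallas telehealth is listed with the same length.

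**Step 2. Which model is the main one?**

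| Place | Model | Survey variables included? |
|---|---|---|
| 9.2.1, primary endpoint | Cox, treatment option as predictor | No |
| 9.2.3, Aims 1-3 paragraph | Cox (Aim 1); GLM with example covariates (Aims 2 and 3) | No |
| 9.2.3, survey paragraph | Analysis under Aims 1-3 | Yes |

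The synopsis labels the survey scores exploratory, and Section 3 labels SA5 exploratory. Neither label mentions Aims 1-3 models that are adjusted for those scores.

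**Step 3. How many events might come before the survey?** The plan gives no figure, so this is an illustration.

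Inputs from Section 9.1: 70 inpatients at a 6-month rate of 19%, and 75 + 75 = 150 telehealth and OCIC patients at 10%. Assumptions: day 0 is baseline, the hazard is constant, six months is 182 days and three months is 91 days. With p the 6-month rate, λ = −ln(1 − p)/182 and F(t) = 1 − exp(−λt).

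- Inpatient: λ = −ln(0.81)/182 = 0.001158. F(14) = 0.01608, so 70 × 0.01608 = 1.13 events. F(91) = 1 − √0.81 = 0.100, so 7.00 events.
- Other two arms: λ = −ln(0.90)/182 = 0.000579. F(14) = 0.00807, so 150 × 0.00807 = 1.21 events. F(91) = 1 − √0.90 = 0.0513, so 7.70 events.
- Total: 2.34 events before day 14 out of 14.70 by day 91, which is 16%.

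Section 8 skips a survey window only after 10 days. If that is read as a return as late as day 24, the count is 3.99 of 14.70 (27%). Using the 27.3% event rate in Section 2.2 for all 220 patients gives 5.33 of 32.42 (16%) at day 14 and 9.06 of 32.42 (28%) at day 24. Under a constant hazard the share is close to elapsed time (14/91 = 15%) and barely depends on the rate. The rates in Section 9.1 are a readmission rate and a reattempt rate, not the composite suicidal event that defines the primary outcome.

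**Step 4. Related point on effect modifiers.** The heterogeneity analysis in Section 9.2.3 lists severity of ideation and substance use both at baseline and across the 180 days of follow-up. The follow-up values arise after treatment, and the synopsis lists ideation severity as an outcome.

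**The case against.** The strongest reply is that the adjusted models are clearly secondary. The survey scores and SA5 are exploratory, the text sits under Other Analyses, Section 9.2.1 gives a primary model without covariates, and Section 9.2 defers detail to an analysis plan finalised before database lock. This makes a supplementary reading plausible. It does not settle the matter, because the main Aims 1-3 models and their power statement sit in the same Section 9.2.3 and the survey sentence carries no label. A later plan would inherit the instruction unless it is corrected.

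The second reply stands in part. A survey given once can yield a change only by recall, and SA5 supposes that "the levels of perceived stress and depressed mood have been increased amidst the COVID-19 pandemic". Some items may therefore describe change before enrolment, and adjusting for that could reduce confounding. The answers are still given after treatment normally starts, and the items cannot be seen.

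It is also fair that unequal treatment stages at week 2 follow from fixed follow-up of treatments of different lengths. That is not an error in itself; it matters only once the value is used as a covariate.

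A reader might infer more than the documents support, in three ways:

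- That events cluster early, so far more than 16% precede the survey, because "Reattempt rates at 6 months were at 8.7%, with almost half these occurring within one month after discharge". That month runs from discharge from OCIC, not from baseline. It says nothing about the first 14 or 24 days, or about the other two arms.
- That the loss in the planned hazard ratio of 2.8 can be calculated. The documents do not say how much of any effect runs through stress or mood.
- That the covariates are the Aim 2 outcome itself. They overlap with SA2's perceived-stress hypothesis. But the Aim 2 model analyses change in emotional arousal at 3 months, which fits the Self-Assessment Manikin schedule (baseline and week 12) rather than a week-2 survey.

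**Conclusion.** The concern holds in a limited form and should be fixed. The plan instructs that survey variables, normally collected after treatment has started, enter the Aims 1-3 treatment-effect models, and it leaves the status of those models open. If setting changes these variables by week 2, the adjusted contrasts are not total effects. For Aim 1, a fixed week-2 value would also be applied to earlier events: about 16% of three-month events before day 14, given a constant hazard, baseline as day 0 and the Section 9.1 rates.

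The size and direction of any bias cannot be derived from the documents. They also do not support saying that the primary analysis is biased as planned, since Section 9.2.1 states it without these covariates.

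**What to change.** In Sections 9.2.1 and 9.2.3:

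- State that the main model for each of Aims 1-3 uses only covariates collected at the baseline visit, and keep them few in the Cox model because events are few. Tying the rule to the baseline visit matters: baseline forms may be completed up to 72 hours after admission, and a strict pre-treatment rule could exclude them.
- Label any model that adds the week-2 survey variables as an exploratory or sensitivity analysis.
- For Aim 1, start that version at the date of survey completion (a landmark), or enter the survey values as time-dependent covariates. Say how patients with an event before the survey, or with no survey, are handled.
- If some items ask about change before enrolment, name them and justify them as confounders.
- In the heterogeneity analysis, use the baseline values of ideation severity and substance use as effect modifiers, not the values over follow-up.

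The cost is a change of wording in the protocol and analysis plan. No new data are needed, and the survey questions can still be studied.
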